#### 8.4.1 Laboratory evaluations

A central laboratory will be used for analysis of all specimens collected.

The central laboratory will flag laboratory values falling outside of the normal ranges on the central laboratory reports. Investigators are responsible for reviewing these abnormal values for clinical significance, signing the laboratory reports to indicate their review, and reporting values considered clinically significant in the appropriate eCRF page.

Clinically significant abnormalities at screening must be recorded as medical history/current medical conditions.

[figure not shown]
Any clinically significant abnormal laboratory value should be evaluated and followed-up by the investigator until normal or a cause for the abnormality is determined.

##### 8.4.1.1 Hematology

Hemoglobin, platelets, white blood cells, differential (basophils, eosinophils, lymphocytes, monocytes, neutrophils, other)

##### 8.4.1.2 Clinical chemistry

Albumin, alkaline phosphatase, serum alanine aminotransferase (ALT), serum aspartate aminotransferase (AST), lactate dehydrogenase (LDH), calcium, magnesium, phosphorus, sodium, potassium, creatinine, direct bilirubin, total bilirubin, urea, uric acid, amylase, lipase, glucose (non-fasting).

### **8.4.1.3 Urinalysis**

Macroscopic (Dipstick) panel - color, bilirubin, blood, glucose, ketones, leukocyte esterase, nitrite, pH, protein, specific gravity, urobilinogen

Microscopic panel - red blood cells, white blood cells, casts, crystals, bacteria and epithelial cells.

### **8.4.2 Electrocardiogram (ECG)**

Electrocardiograms must be recorded after 10 minutes rest in the supine position to ensure a stable baseline. The preferred sequence of cardiovascular data collection during study visits is ECG collection first, followed by vital signs, and blood sampling. The Fridericia QT correction formula should be used for clinical decisions.

A single 12-lead ECG is collected. The original ECGs on non-heat-sensitive paper or a certified copy on non-heat sensitive paper, appropriately signed, must be collected and archived at the study site. If a patient had an ECG performed within 6 months of screening, the results of this ECG can be used in lieu of performing the screening ECG. A copy of the historical ECG will be retained in the patient's source documentation.

[figure not shown]
Clinically significant abnormalities must be recorded on the eCRF as either medical history/current medical conditions or adverse events as appropriate.

### **8.4.3 Pregnancy and assessments of fertility**

All pre-menopausal women who are not surgically sterile will have pregnancy testing. Additional pregnancy testing might be performed if requested by local requirements. A serum pregnancy test is performed at screening and a urinary pregnancy test is sufficient at the end of study visit.

### **8.4.4 Appropriateness of safety measurements**

The safety assessments selected are appropriate evaluations of ocular and systemic health in presbyopic subjects administered UNR844-CI ophthalmic solution.

## 9 Study discontinuation and completion

### 9.1 Discontinuation

#### 9.1.1 Discontinuation of study treatment

Discontinuation of study treatment for a subject occurs when study treatment is stopped earlier than the protocol planned duration, and can be initiated by either the subject or the investigator.

The investigator must discontinue study treatment for a given subject if, he/she believes that continuation would negatively impact the subject's well-being.

Study treatment must be discontinued under the following circumstances:

- Subject decision
- Pregnancy
- Use of prohibited medications or therapies as described in [Table 6-2](#)
- Unsatisfactory therapeutic effect
- Any situation in which study participation might result in a safety risk to the subject
- Following emergency unmasking

If discontinuation of study treatment occurs, the investigator should make a reasonable effort to understand the primary reason for the subject's premature discontinuation of study treatment and record this information.

Subjects who discontinue study treatment or who decide they do not wish to participate in the study further should NOT be considered withdrawn from the study UNLESS they withdraw their consent (see [Section 9.1.2](#)). **Where possible, they should return for the assessments indicated in the assessment schedule.** If they fail to return for these assessments for unknown reasons, every effort (e.g., telephone, e-mail, or letter) should be made to contact the subject/pre-designated contact as specified in the lost to follow-up section. This contact should preferably be done according to the study visit schedule.

If the subject cannot or is unwilling to attend any visit(s), the site staff should maintain regular telephone contact with the subject, or with a person pre-designated by the subject. This telephone contact should preferably be done according to the study visit schedule.

After study treatment discontinuation, at a minimum, in abbreviated visits, the following data should be collected at clinic visits or via telephone/email contact:

- New/concomitant treatments
- AEs/SAEs

The investigator must also contact the IRT to register the subject's discontinuation from study treatment.

If discontinuation occurs because treatment code has been broken, please refer to Emergency breaking of treatment code section ([Section 6.6.2](#)).

### **9.1.2 Withdrawal of informed consent**

Subjects may voluntarily withdraw consent to participate in the study for any reason at any time. Withdrawal of consent occurs only when a subject:

- Does not want to participate in the study anymore, AND
- Does not allow further collection of personal data, AND
- Does not want any further study-related contacts

In this situation, the investigator should make a reasonable effort (e.g., telephone, e-mail, letter) to understand the primary reason for the subject's decision to withdraw his/her consent and record this information.

Study treatment must be discontinued and no further assessments conducted, and the data that would have been collected at subsequent visits will be considered missing.

Further attempts to contact the subject are not allowed unless safety findings require communicating or follow-up.

All efforts should be made to complete the assessments prior to study withdrawal. A final evaluation at the time of the subject's study withdrawal should be made as detailed in the assessment table ([Table 8-1](#)).

Novartis will continue to retain and use all research results (data) that have already been collected for the study evaluation.

### **9.1.3 Lost to follow-up**

For subjects whose status is unclear because they fail to appear for study visits without stating an intention to discontinue or withdraw, the investigator must show "due diligence" by documenting in the source documents steps taken to contact the subject (e.g., dates of telephone calls, registered letters). A subject should not be considered as lost to follow-up until due diligence has been completed or until the end of the study.

### **9.1.4 Early study termination by the sponsor**

The study can be terminated by Novartis at any time for any reason. This may include reasons related to the benefit/risk assessment of participating in the study, practical reasons (including slow enrollment), or for regulatory or medical reasons. In taking the decision to terminate, Novartis will always consider the subject welfare and safety. Should early termination be necessary, subjects must be seen as soon as possible (provide instruction for contacting the

subject, when the subject should stop taking drug, when the subject should come for a final visit) and treated as a prematurely withdrawn subject. The investigator may be informed of additional procedures to be followed in order to ensure that adequate consideration is given to the protection of the subject's interests. The investigator or sponsor depending on the local regulation will be responsible for informing IRBs of the early termination of the trial.

## **9.2 Study completion and post-study treatment**

Study completion is defined as when the last subject finishes their Study Completion visit, and any repeat assessments associated with this visit have been documented and followed-up appropriately by the Investigator, or in the event of an early study termination decision, the date of that decision.

All randomized and/or treated subjects should have a safety follow-up call conducted 30 days after last administration of study treatment. The information collected is kept as source documentation. All SAEs reported during this time period must be reported as described in [Section 10.1.3](#). Documentation of attempts to contact the subject should be recorded in the source documentation.

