**Table 8-2 Safety assessment specifications**

Assessment	Specification
Physical examination	A routine physical examination will be performed at the baseline visit and will include an evaluation of the general appearance (e.g., skin, peripheral blood perfusion, extremities, lymph nodes).

[REDACTED]

Assessment	Specification
	Information for all physical examinations should be included in the source documentation at the study site. Clinically relevant findings that are present prior to signing informed consent must be included in the Medical History part of the eCRF. Significant findings made after first administration of investigational drug that meet the definition of an Adverse Event must be recorded on the Adverse Event section of the eCRF.
Vital sign	Vital signs include blood pressure (BP) and heart rate measurements. After the patient has been sitting for five minutes, with back supported and both feet placed on the floor, systolic and diastolic BPs will be measured once using an automated validated device (e.g., OMRON) with an appropriately sized cuff. If the investigator has any concerns with the single measurement, BP measurements should then be repeated after at least 10 minutes from the first measurement. All individual measurements should be entered in the source document. In case the cuff sizes available are not large enough for the patient's arm circumference, a sphygmomanometer with an appropriately sized cuff may be used.
Best-corrected distance visual acuity (BCDVA)	BCDVA will be measured binocularly and monocularly at 100% contrast at 4 m at the visits as detailed in the assessment schedule. An electronic visual acuity testing system will be used for this assessment.

Assessment	Specification

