Ophthalmic Examination	The following ocular assessments will be performed as per the schedule assessment: 

1. Slit-lamp examination include evaluation of the lids/lashes, conjunctiva, cornea, anterior chambers aqueous reactions (cells and flare), iris, lens and anterior part of the vitreous body and assessment of phacodonesis in both eyes. Slit-lamp examination will be performed before study treatment and throughout the study. Phacodonesis should be assessed after dilation at Screening and Month 3 visits. The results will be recorded in the source documents only and any clinically significant findings must be documented in the eCRF.

2. Intraocular pressure will be assessed in both eyes with Goldmann applanation tonometer or Tonopen. This assessment must be performed after any visual acuity assessments.

3. Dilated fundus examination will be performed in both eyes. Any clinically significant findings must be documented in the eCRF.

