## **10 Safety monitoring and reporting**

### **10.1 Definition of adverse events and reporting requirements**

#### **10.1.1 Adverse events**

An AE is any untoward medical occurrence (e.g., any unfavorable and unintended sign (including abnormal laboratory findings), symptom or disease) in a subject or clinical investigation subject after providing written informed consent for participation in the study. Therefore, an AE may or may not be temporally or causally associated with the use of a medicinal (investigational) product.

The investigator has the responsibility for managing the safety of individual subject and identifying AEs.

Novartis qualified medical personnel will be readily available to advise on trial-related medical questions or problems.

The occurrence of AE must be sought by non-directive questioning of the subject at each visit during the study. Adverse events also may be detected when they are volunteered by the subject during or between visits or through physical examination findings, laboratory test findings, or other assessments.

Adverse events must be recorded in the Adverse Events eCRF under the signs, symptoms or diagnosis associated with them, accompanied by the following information (as far as possible) (if the event is serious refer to [Section 10.1.2](#)):

1. The severity grade
  - Mild: usually transient in nature and generally not interfering with normal activities
  - Moderate: sufficiently discomforting to interfere with normal activities
  - Severe: prevents normal activities

2. Its relationship to the study treatment
  - If the event is due to lack of efficacy or progression of underlying illness (i.e., progression of the study indication) the assessment of causality will usually be ‘Not suspected’. The rationale for this guidance is that the symptoms of a lack of efficacy or progression of underlying illness are not caused by the trial drug, they happen in spite of its administration and/or both lack of efficacy and progression of underlying disease can only be evaluated meaningfully by an analysis of cohorts, not on a single subject
3. Its duration (start and end dates) or if the event is ongoing, an outcome of not recovered/not resolved must be reported.
4. Whether it constitutes a SAE (see [Section 10.1.2](#) for definition of SAE) and which seriousness criteria have been met

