5. Action taken regarding with study treatment. All adverse events must be treated appropriately. Treatment may include one or more of the following:
  - dose not changed
  - drug interrupted/withdrawn
6. Its outcome (i.e., its recovery status or whether it was fatal)

Conditions that were already present at the time of informed consent should be recorded in medical history of the subject.

Adverse events (including lab abnormalities that constitute AEs) should be described using a diagnosis whenever possible, rather than individual underlying signs and symptoms.

Adverse event monitoring should be continued for at least 30 days (or end of study visit, whichever is longer) following the last dose of study treatment.

Once an adverse event is detected, it must be followed until its resolution or until it is judged to be permanent (e.g., continuing at the end of the study), and assessment must be made at each visit (or more frequently, if necessary) of any changes in severity, the suspected relationship to the study treatment, the interventions required to treat it, and the outcome.

Information about adverse drug reactions for the investigational drug can be found in the IB.

[figure not shown]
Abnormal laboratory values or test results constitute AEs only if they fulfill at least one of the following criteria:

- They induce clinical signs or symptoms
- They are considered clinically significant
- They require therapy

Clinically significant abnormal laboratory values or test results must be identified through a review of values outside of normal ranges/clinically notable ranges, significant changes from baseline or the previous visit, or values, which are considered to be non-typical in subjects with the underlying disease.

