### **10.1.3 SAE reporting**

To ensure subject safety, every SAE, regardless of causality, occurring after the subject has provided informed consent and until 30 days following the last administration of study treatment must be reported to Novartis Safety within 24 hours of learning of its occurrence. Detailed instructions regarding the submission process and requirements are to be found in the investigator site file provided to each site.

All follow-up information for the SAE including information on complications, progression of the initial SAE and recurrent episodes must be reported as follow-up to the original episode within 24 hours of the investigator receiving the follow-up information. An SAE occurring at a different time interval or otherwise considered completely unrelated to a previously reported one must be reported separately as a new event.

If the SAE is not previously documented in the IB (i.e., a new occurrence) and is thought to be related to the study treatment, a Novartis Safety Department associate may urgently require further information from the investigator for health authority reporting. Novartis may need to issue an Investigator Notification to inform all investigators involved in any study with the same study treatment that this SAE has been reported.

Suspected Unexpected Serious Adverse Reactions (SUSARs) will be collected and reported to the competent authorities and relevant ethics committees as per national regulatory requirements in participating countries.

Any SAEs experienced after the 30-day period following the last administration of study treatment should only be reported to Novartis Safety if the investigator suspects a causal relationship to study treatment.

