### 11.2 Database management and quality control

Novartis personnel or designated contract research organization (CRO) will review the data entered by investigational staff for completeness and accuracy. Electronic data queries stating the nature of the problem and requesting clarification will be created for discrepancies and missing values and sent to the investigational site via the EDC system. Designated investigator

site staff are required to respond promptly to queries and to make any necessary changes to the data.

Concomitant treatments and prior medications entered into the database will be coded using the World Health Organization Drug Reference List, which employs the Anatomical Therapeutic Chemical (ATC) classification system. Medical history/current medical conditions and adverse events will be coded using the Medical dictionary for regulatory activities (MedDRA) terminology.

Randomization codes and data about all study treatment(s) dispensed to the subject will be tracked using IRT. The system will be supplied by a vendor, who will also manage the database. The data will be sent electronically to Novartis (or a designated CRO) at specific timelines.

Each occurrence of a code break via IRT will be reported to Novartis personnel. The code break functionality will remain available until study shut down or upon request of Novartis.

Once all the necessary actions have been completed and the database has been declared to be complete and accurate, it will be locked and the treatment codes will be unmasked and made available for data analysis. Any changes to the database after that time can only be made after written agreement by Novartis development management.

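### Does keeping the 30-day call as source documentation leave late non-serious adverse events out of the TEAE counts?

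*Protocol*

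**What the plan says.** Protocol 12.5.2 and SAP 2.1.1.5 and 2.8.1 define TEAEs as events that start between the first dose and 30 days after the last dose. Their frequency is a secondary safety endpoint, summarised descriptively.

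Protocol 9.2 schedules a safety call 30 days after the last dose. It then says "The information collected is kept as source documentation" and "All SAEs reported during this time period must be reported as described in" Section 10.1.3. It does not mention the Adverse Events eCRF.

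Protocol 10.1.1 gives the general rule: "Adverse events must be recorded in the Adverse Events eCRF under the signs, symptoms or diagnosis associated with them". It also says "Adverse event monitoring should be continued for at least 30 days" after the last dose. Neither statement is limited to serious events. Section 8.4 refers the reader to Section 10.1 for adverse event collection and reporting.

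Section 10.1.3 separately covers serious events "occurring after the subject has provided informed consent and until 30 days following the last administration of study treatment".

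On lock, Section 11.2 says "Once all the necessary actions have been completed and the database has been declared to be complete and accurate, it will be locked". It does not list the steps that must come first.

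**The concern.** The last scheduled adverse event assessment in Table 8-1 is the Month 3 visit at Day 90, and the table has no column for the call. For a completer, the final 30 days of the TEAE window therefore rest mainly on that call and on whatever the subject volunteers. Section 9.2 places the call's content in source and singles out serious events.

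Elsewhere the protocol pairs source with an eCRF instruction. In Table 8-2, physical examination findings "that meet the definition of an Adverse Event must be recorded on the Adverse Event section of the eCRF", and for the slit lamp "The results will be recorded in the source documents only and any clinically significant findings must be documented in the eCRF". Section 9.2 has no such pairing, so a site reading it in isolation might leave non-serious events in its own files. Analysts cannot recover an event that was never entered, and reported TEAE frequencies would then be too low for the stated window.

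**Working it through.** **Share of the window exposed.** The documents give no expected TEAE rate, so there is no planned figure to reproduce. SAP 2.1.1.5 sets the window at last dose day − first dose day + 1 + 30. With first dose on Day 1, last dose on Day d and the final visit on Day 90, the days after the visit are max(0, d + 30 − 90).

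| Last dose day | Window (days) | Days after Day 90 | Share |
|---|---|---|---|
| 90 | 90 − 1 + 1 + 30 = 120 | 30 | 25.0% |
| 75 | 75 − 1 + 1 + 30 = 105 | 15 | 14.3% |
| 60 | 60 − 1 + 1 + 30 = 90 | 0 | 0% |

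The last two rows assume that contacts under Section 9.1.1 continue to Day 90. Section 5 expects 66 + 44 = 110 completers, so at most 110 × 30 = 3,300 of 110 × 120 = 13,200 subject-days are involved. These are calendar days, not missed events.

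**Worst-case illustration.** Section 4.5 reports nasopharyngitis in 16% (active) and 8% (placebo) of subjects in the prior study. Assume that these rates cover 90 days at constant hazard, that 110 / 2 = 55 subjects per arm complete, and that no site enters any event after the last visit. The full-window share is 1 − (1 − p)^(120/90).

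- Active: 1 − 0.84^(120/90) = 20.74%, so 4.74 points missed; 55 × 0.0474 = 2.6 subjects.
- Placebo: 1 − 0.92^(120/90) = 10.52%, so 2.52 points missed; 55 × 0.0252 = 1.4 subjects.
- If the hazard halves after the last dose, the exponent is (90 + 15)/90 = 105/90. The losses become 18.41% − 16% = 2.41 points and 9.27% − 8% = 1.27 points.

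The lower limit is zero in every case.

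**Does the text permit that loss?** Four comparisons say no.

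1. *Scope of the general rule.* The eCRF rule in 10.1.1 is not restricted by seriousness or by type of contact. The same section recognises events volunteered between visits and keeps monitoring open through the day of the call. A non-serious event learned then falls within it.
2. *Meaning of source.* Section 11.3 requires eCRF content to be traceable to source documents, so a source record is the normal step before entry. Where the documents mean that data stop at source, they say so: the slit-lamp item in Table 8-2 uses the word *only*, and SAP 2.8.3 and 2.8.4.1 drop laboratory and ECG analyses on that stated ground. Section 9.2 contains no such restriction.
3. *The Table 8-2 contrast.* The vital-signs row also sends individual measurements to source and adds no eCRF sentence. Yet Protocol 12.5.2 and SAP 2.8.4.2 list and summarise all vital signs data. Within this plan, then, a source instruction without an eCRF instruction does not keep data out of the database.
4. *Why serious events are named.* The sentence in 9.2 points to 10.1.3, the 24-hour report to the sponsor's safety group. Naming the events that need expedited reporting does not narrow routine recording.

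**The case for a change.** The best argument for the concern is lock timing. Section 9.2 defines study completion by the last subject's final visit rather than by the call, Section 12 places the analysis when the study ends, and no section names the last call as a step before lock. A site could follow 10.1.1 faithfully and still have its last events arrive too late. Section 9.1.1 adds some weight, because for contacts after treatment discontinuation it names both adverse events and serious adverse events, whereas 9.2 names only the latter.

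The silence on lock is real. But Section 11.2 allows lock only after the database has been declared complete and accurate, and a database that lacks the last 30 days of required monitoring is not complete against 10.1.1 or against the TEAE window in 12.5.2. Data management would have to lock against the plan's own definitions for the loss to occur. The wording difference between 9.1.1 and 9.2 shows uneven drafting. It does not set aside the general rule.

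**Conclusion.** The concern does not call for a change. Section 9.2 is loosely worded beside 10.1.1, but together the sections already require non-serious events learned at the call to be entered in the eCRF and counted. This is a gap in wording that sites, data managers and analysts fill correctly by following the rest of the plan. Extra sentences in 9.2 or 11.2 would only restate existing duties.

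Followed in full, the plan gives an undercount of zero. The upper figures above (4.7 and 2.5 points for one event term) need every site to omit every late event, and they also rest on assumed rates and timing. The true size cannot be derived from the documents. Serious events are protected by 10.1.3, efficacy is unaffected, and masking with the same call in both arms gives no reason to expect a difference between arms. The conclusion assumes that sites follow 10.1.1 at the call and that lock follows entry of the last calls.
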